## Appendix 2: Liver event and laboratory trigger definitions & 16.2 follow-up requirements

**Table 16-1** Liver event and laboratory trigger definitions

Novartis

able 10-1 Livel event and laboratory trigger definitions		
	Definition/ threshold	
Liver laboratory triggers	ALT or AST > 5 × ULN	
If ALT, AST and total bilirubin normal at baseline:	
 
ALP > 2 × ULN (in the absence of known bone pathology)
 
	
	
 
Total bilirubin > 3 × ULN (in the absence of known Gilbert syndrome)
 
	
	
 
ALT or AST > 3 × ULN and INR > 1.5
 
	
	
 
Potential Hy's Law cases (defined as ALT or AST > 3 × ULN and Total bilirubin > 2 × ULN [mainly conjugated fraction] without notable increase in ALP to > 2 × ULN)
 
	
	
 
Any clinical event of jaundice (or equivalent term)
 
	
	
 
ALT or AST > 3 × ULN accompanied by (general) malaise, fatigue, abdominal pain, nausea, or vomiting, or rash with eosinophilia
 
	
	
 
Any adverse event potentially indicative of a liver toxicity
 
	

ALP: Alkaline phosphatase, ALT: Alanine aminotransferase, AST: Aspartate aminotransferase, ULN: upper limit of normal

Follow up requirements for liver laboratory triggers: ALT, AST and **Table 16-2** TBL

		Action Taken		
Trigger	Liver Symptoms	Monitoring	Follow-up Monitoring	Study Medication
ALT				
ALT > 3 ULN TBL normal, or no change for participants with Gilbert's syndrome	None	Measure ALT, AST, ALP, GGT, TBL, INR, albumin, CK, and GLDH in 48-72 hours	Follow up for symptoms	Continue dosing
ALT > 5 x ULN for more than two weeks TBL normal, or no change for participants with Gilbert's syndrome	None	Measure ALT, AST, ALP, GGT, TBL, INR, albumin, CK, and GLDH in 48-72 hours	Follow-up for symptoms Initiate close monitoring and workup for competing etiologies	Interrupt Study drug can be restarted only if another etiology is identified and liver enzymes return to baseline
ALT > 8 x ULN TBL normal, or no change for participants with Gilbert's syndrome	None	Measure ALT, AST, ALP, GGT, TBL, INR, albumin, CK, and GLDH in 48-72 hours	Follow-up for symptoms Initiate close monitoring and workup for competing etiologies	Interrupt Study drug can be restarted only if another etiology is identified and liver enzymes return to baseline

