ALT > 3 x ULN TBL > 2 x ULN (or INR > 1.5) For patients with	None	Measure ALT, AST, ALP, GGT, TBL, INR, albumin, CK,	Follow-up for symptoms Initiate close monitoring and	Interrupt Study drug can be restarted only if another etiology is

		Action Taken		
Trigger	Liver Symptoms	Monitoring	Follow-up Monitoring	Study Medication
Gilbert's syndrome: Doubling of direct bilirubin		and GLDH in 48-72 hours	workup for competing etiologies	identified and liver enzymes return to baseline
ALT > 3 x ULN TBL normal or elevated	Severe fatigue, nausea, vomiting, right upper quadrant pain	Measure ALT, AST, ALP, GGT, TBL, INR, albumin, CK, and GLDH in 48-72 hours	Follow-up for symptoms Initiate close monitoring and workup for competing etiologies	Interrupt Study drug can be restarted only if another etiology is identified and liver enzymes return to baseline
Total Bilirubin (isola	ated)			
>1.5 – 3.0 ULN		Repeat LFTs within 48-72 hours	Monitor LFTs weekly until resolution¹ to ≤ Grade 1 or to baseline	Continue dosing
> 3 - 10 × ULN (in the absence of known Gilbert syndrome)		Repeat LFT within 48-72 hours Hospitalize if clinically appropriate Establish causality Record the AE and contributing factors (e.g., conmeds, med hx, lab) in the appropriate CRF	Monitor LFTs weekly until resolution¹ to ≤ Grade 1 or to baseline (ALT, AST, total bilirubin, Alb, PT/INR, ALP and GGT) Test for hemolysis (e.g., reticulocytes, haptoglobin, unconjugated [indirect] bilirubin)	Interrupt
> 10 x ULN		Hospitalize the participant Establish causality Record the AE and contributing factors(e.g., conmeds, med hx, lab) in the appropriate CRF	ALT, AST, total bilirubin, Alb, PT/INR, ALP and GGT until resolution  (frequen cy at investigator discretion)	Discontinue treatment immediately
General Clinical Syr	mptoms			
Any AE potentially inc toxicity including: (Ge fatigue, abdominal pa vomiting, or rash with	eneral) malaise, ain, nausea, or	Establish causality Record the AE and contributing factors(e.g., conmeds, med hx, lab) in the appropriate CRF	Investigator discretion	Consider study treatment interruption or discontinuation

<sup>1Resolution is defined as an outcome of one of the following: (1) return to baseline values, (2) stable values at three subsequent monitoring visits at least 2 weeks apart, (3) remain at elevated level after a maximum of 6 months, (4) liver transplantation, and (5) death

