Alb: Albumin, ALP: Alkaline phosphatase, ALT: Alanine aminotransferase, AST: Aspartate aminotransferase, CK: Creatinine kinase, CRF: Case report form, GGT: Gamma-glutamyl transferase, GLDH: glutamate dehydrogenase, INR: International Normalized Ratio, LFTs: Liver function tests, Med Hx: medical history, PT: Prothrombin time, TBL: Total bilirubin, ULN: upper limit of normal

Criteria	Actions required	Follow-up monitoring
Total Bilirubin (isolated)	·	
>1.5 - 3.0 ULN	- Maintain treatment- Repeat LFTs within 48-72 hours	Monitor LFTs weekly until resolution to ≤ Grade 1 (≤ 1.5 ULN) or to baseline
> 3 - 10 x ULN (in the absence of known Gilbert syndrome)	
 
Interrupt treatment
 
Repeat LFT within 48-72 hours
 
Hospitalize if clinically appropriate
 
Establish causality
 
Record the AE and contributing factors(e.g., conmeds, med hx, lab) in the appropriate CRF
 
	- Monitor LFTs weekly until resolution to ≤ Grade 1 (≤ 1.5 ULN) or to baseline (ALT, AST, total bilirubin, Alb, PT/INR, ALP and GGT) - Test for hemolysis (e.g., reticulocytes, haptoglobin, unconjugated [indirect] bilirubin)
> 10 x ULN	
 
Discontinue the study treatment immediately
 
Hospitalize the participant
 
Establish causality
 
Record the AE and contributing factors(e.g., conmeds, med hx, lab)in the appropriate CRF
 
	ALT, AST, total bilirubin, Alb, PT/INR, ALP and GGT until resolution (frequency at investigator discretion)
Any AE potentially indicative of a liver toxicity	
 
Consider study treatment interruption or discontinuation
 
Hospitalization if clinically appropriate- Establish causality- Record the AE and contributing factors (e.g., conmeds, med hx, lab) in the appropriate CRF
 
	Investigator discretion

Based on investigator's discretion investigation(s) for contributing factors for the liver event can include: Serology tests, imaging and pathology assessments, hepatologist's consultancy; obtaining more detailed history of symptoms and prior or concurrent diseases, history of concomitant drug use, exclusion of underlying liver disease.

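### Protocol Table 16-2 mandates interruption for potential Hy's Law, INR and symptomatic liver events only when ALT is raised, although Table 16-1 defines those events on ALT or AST

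*Protocol*

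**What the plan says.** Table 16-1 (Protocol Section 16.2) lists the liver triggers. Three of them combine a transaminase above 3×ULN with a second sign, and each accepts either enzyme:

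- ALT or AST with INR above 1.5.
- "Potential Hy's Law cases (defined as ALT or AST" above 3×ULN, with total bilirubin (TBL) above 2×ULN, mainly conjugated, and no notable ALP rise above 2×ULN.
- ALT or AST "accompanied by (general) malaise, fatigue, abdominal pain, nausea, or vomiting, or rash with eosinophilia".

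Section 10.2.1 sends the site to Tables 16-2 and 16-3 for the actions required. The caption of Table 16-2 names both enzymes, "Follow up requirements for liver laboratory triggers: ALT, AST and" TBL. Its two rows for combined events start from ALT only. One begins "ALT > 3 x ULN TBL > 2 x ULN (or INR > 1.5". The other reads "ALT > 3 x ULN TBL normal or elevated", with severe fatigue, nausea, vomiting or right upper quadrant pain as the symptom. Both rows order interruption and add: "Study drug can be restarted only if another etiology is identified and liver enzymes return to baseline".

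The bilirubin rows in both tables stand under a heading that begins "Total Bilirubin (isolated". The row for general liver symptoms and adverse events says "Consider study treatment interruption or discontinuation".

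**The concern.** A site that follows the tables as written treats the same clinical event differently according to which enzyme is raised. If ALT is above 3×ULN, the drug must be interrupted and cannot be restarted without another explanation. If only AST is, the participant can stay on drug on the investigator's judgment, or restart without any other cause being found.

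SAP Table 2-9 counts the combined liver abnormalities on ALT or AST. A participant can therefore be tabulated as a potential Hy's Law case while the protocol row written for that event does not apply. No estimate in the SAP is biased by this. What is at stake is exposure during a possible drug-induced liver injury, and re-exposure after it, in a study whose primary objective is safety.

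**Working it through.** The plan states no figure here to reproduce. The check sets the triggers beside the action rows, then looks for any other text that extends mandatory interruption to AST.

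**Step 1: triggers against action rows.** AST column: AST above 3×ULN, ALT not above 3×ULN.

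| Second sign | Table 16-1 trigger | Action when ALT >3×ULN | Action when only AST >3×ULN |
|---|---|---|---|
| TBL >2 to 3×ULN | ALT or AST | Interrupt, cause-based restart rule | No transaminase row. The bilirubin row for that value, under the isolated heading, says to carry on dosing (both tables) |
| INR >1.5 | ALT or AST | Interrupt, cause-based restart rule | No row |
| Severe symptom named in the row | ALT or AST | Interrupt, cause-based restart rule | Liver adverse-event row: consider only |

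Mandatory interruption with the cause-based restart rule: 3 of 3 for ALT, 0 of 3 for AST alone.

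**Step 2: an illustration (values assumed).** Take AST 4×ULN, ALT 2×ULN, TBL 2.5×ULN (mainly conjugated) and normal ALP. Table 16-1 and SAP Table 2-9 both make this a potential Hy's Law case. No transaminase row of Table 16-2 is met, because ALT is not above 3×ULN. Replace the raised TBL with INR 1.6 and it is still a Table 16-1 trigger with no action row.

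**Step 3: the edges of the gap.**

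- At TBL above 3 to 10×ULN the bilirubin row says to interrupt, but it too is headed isolated and has no cause-based restart rule. Above 10×ULN treatment is discontinued. The clear gap for bilirubin is therefore above 2 and up to 3×ULN.
- Table 16-1 has six symptom terms: malaise, fatigue, abdominal pain, nausea, vomiting, and rash with eosinophilia. The Table 16-2 row has four: severe fatigue, nausea, vomiting and right upper quadrant pain. Malaise and rash with eosinophilia (2 of 6) have no mandatory row even for ALT, so the comparison uses only the row's own terms.

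**Step 4: other text that might cover AST.**

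- Section 10.2.1 asks for repeat chemistry and, if the rise is confirmed, close observation with interruption to be considered.
- Section 9.1.1 requires discontinuation where continuing might put the participant at risk. This rests on judgment. Its liver-laboratory item refers back to Section 16.2.
- Section 6.6 allows other interruptions on the investigator's opinion, with restart at the next scheduled visit once the safety risk has resolved. It does not ask for another cause.
- Table 16-3, as extracted, has only bilirubin and liver adverse-event rows.

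None of these makes interruption automatic for AST or carries over the restart rule.

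**Step 5: the SAP.** Table 2-9 has three lines that combine a transaminase with TBL or INR: with TBL, with INR, and with TBL and ALP. All 3 of 3 use ALT or AST. Its separate ALT-only line concerns isolated rises.

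**The case against.** The strongest reply is that Table 16-2 was never a row-by-row answer to Table 16-1. Table 16-1 triggers at ALT or AST above 5×ULN, whereas Table 16-2 interrupts at ALT above 5×ULN only after more than two weeks. ALP rises and jaundice are triggers with no row of their own. On this reading Table 16-1 says what to follow up, mandatory interruption covers a narrower set, and five ALT-only rows under an ALT heading could be deliberate, since AST can rise for non-hepatic reasons. Those differences are real. They do not explain dropping AST from combined events when the caption, Table 16-1 and all three SAP lines include it, and no reason is given.

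The second reply is that protection exists. Section 9.1.1 has a low threshold and leads to permanent discontinuation, and Section 6.6 does not allow restart while the risk persists. Both points stand and limit the harm. They leave to judgment what is automatic for ALT, and neither supplies the requirement to find another cause.

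Third, a bilirubin row headed isolated should not be applied to someone with raised AST. That is the better reading. Even so, it leaves no mandatory row, and a site looking up the bilirubin value alone would find an instruction to continue.

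Fourth, such events will be rare. Hepatotoxicity is not among the potential risks in Section 4.5, hepatic disease and AST or ALT above 1.5×ULN at screening are excluded, chemistry is measured at every scheduled visit, and a data monitoring committee reviews safety. This is accepted; the number affected could be zero.

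Lastly, an AST block might have been lost when the tables were read from PDF. The ALT rows run straight into the bilirubin rows, so this is unlikely but not excluded.

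**Conclusion.** The concern holds. For AST-driven events with TBL above 2 and up to 3×ULN, INR above 1.5, or a severe symptom named in the row, the protocol mandates neither interruption nor the cause-based restart rule, while the same event driven by ALT gets both. The 3 of 3 against 0 of 3 comparison counts table rules, not patients. Few of about 70 participants would be affected, and the documents do not allow a rate to be estimated. The statistical analysis is unaffected.

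This should be corrected because the remedy is small and the events are those for which continued exposure matters most. The conclusion assumes that the extracted tables are complete.

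**What to change.** In Table 16-2, replace ALT above 3×ULN with ALT or AST above 3×ULN in two rows, the combined TBL/INR row and the severe-symptoms row, and keep the existing restart rule. Issue it as a protocol amendment with a memo to sites. If dosing here has ended, check the same rows in the protocol of the extension study under consideration.

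No scheduled assessment is added. An AST-driven event would get the row's panel at 48–72 hours: ALT, AST, ALP, GGT, TBL, INR, albumin, CK and GLDH, 9 tests. Section 10.2.1 already orders 6 of these for every Table 16-1 event (ALT, AST, TBL, PT/INR, ALP, GGT). The additions are therefore 9 − 6 = 3 tests (albumin, CK, GLDH) and the time limit.

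The cost is an occasional interruption for an AST rise that proves non-hepatic. It is limited because both rows also need raised bilirubin, raised INR or severe symptoms, because CK and GLDH help find the source, and because restart is allowed once another cause is identified and liver enzymes are back at baseline. Whether to extend the isolated ALT rows above 5× and 8×ULN to AST is a closer trade-off, since no second sign is required there. That is for the sponsor's safety team.

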# 16.3 Appendix 3: Specific Renal Alert Criteria and Actions and Event Follow-up

Table 16-4 Specific renal alert criteria and actions

Renal Event	Actions		
Confirmed serum creatinine increase 25 – 49%	Consider causes and possible interventions		
	
 
Follow -up within 2-5 days; increase fluid intake before assessment if appropriate
 
		
	
 
Repeat follow-up (every 2-5 days) until creatinine is <125% of baseline value
 
		
Serum creatinine increase  50 % 	
 
Consider causes and possible interventions and initiate renal investigation
 
		
	
 
Repeat assessment within 24-48 h if possible
 
		
	Interruption of study drug		
	
 
Close follow-up (every 24-48 h), consider participant hospitalization and specialized treatment until creatinine is <125% of baseline value
 
		
New onset dipstick proteinuria ≥ 3 	
 
Consider causes and possible interventions
 
		
When urine proteins are measured as a follow-	Assess serum albumin & serum total protein		
up of positive urine dipstick measurements:Protein-creatinine ratio (PCR) ≥	Repeat assessment to confirm		
1 g/g Cr (or mg/mmol equivalent as converted by the measuring laboratory)	
 
Consider drug interruption or discontinuation unless other causes are diagnosed and corrected
 
		
New onset hematuria ≥ 3¹ on urine dipstick	Assess and document		
	Repeat assessment to confirm		
	Distinguish hemoglobinuria from hematuria		
	Urine sediment microscopy		
	Assess sCr		
	
 
Exclude infection, trauma, bleeding from the distal urinary tract/bladder, menstruation
 
		
	Consider bleeding disorder		

<sup>1 Corresponds to KDIGO criteria for Acute Kidney Injury

Whenever a renal event is identified, a detailed participant history and examination are indicated to identify and potentially eliminate risk factors that may have initiated or contributed to the event:

- Blood pressure assessment (after 5-minute rest, with an appropriate cuff size)
- Signs and symptoms like fever, headache, shortness of breath, back or abdominal pain, dysuria or hematuria, dependent or periorbital edema
- Changes in blood pressure, body weight, fluid intake, voiding pattern, or urine output
- Concomitant events or procedures such as trauma, surgical procedures, cardiac or hepatic failure, contrast media or other known nephrotoxin administration, or other diseases or causes, eg, dehydration due to delirium, tumor lysis

#### Table 16-5 Renal event follow-up

#### **FOLLOW-UP OF RENAL EVENTS**

Assess, document and record in the CRF:

- Urine dipstick and sediment microscopy evidence of Drug-Induced Nephrotoxicity (DIN): crystals, red blood cells (dysmorphic/glomerular vs. non-dysmorphic/non-glomerular), white blood cells, tubular epithelial cells
- · Blood pressure and body weight
- Serum creatinine, BUN, electrolytes (sodium, potassium, phosphate, calcium), bicarbonate and uric acid
- Urine output

Review and record possible contributing factors to the renal event (co-medications, other co-morbid conditions) and additional diagnostic procedures (MRI etc.) in the CRF

Monitor participant regularly (frequency at investigator's discretion) until:

- Event resolution: (sCr within 10% of baseline or PCR < 1 g/g Cr, or ACR <300 mg/g Cr) or
- Event stabilization: sCr level with ±10% variability over last 6 months or protein-creatinine ratio stabilization at a new level with ±50% variability over last 6 months.

Analysis of urine markers in samples collected over the course of the DIN event

|---------------------|----------------------------|---|-----------------------|--|
| 10- Apr- 2023 | Prior to the primary | In general the SAP was amended to | SAP Amendment 2 | Section 1 update reference document version |
| | analysis | align with LOU064A2301 and LOU064A2302 | | Section 2.4.2 combine the summary of concomitant medications for urticaria and non-urticaria |
| | | studies Adress the discrepancy between SAP | | Section 2.5.2 add analyses of exposure adjusted incidence rates for adverse events and serious adverse events |
| | | Add new safety analyses | | Section 2.6.1 add the handling of duplicated data in eDiary |
| | | | | Section 2.7.3 add the handling of urinalysis central laboratory data Update the CTCAE grade based on internal guidance (Version 5.0) Add graphical presentation for liver enzyme test abnormalities |
| | | | | |
| | | | | Section 2.12 add detail of the conversion factor document |
| | | | | Section 5.4.1.1 new section of exposure adjusted incidence rate |
| | | | | Section 5.4.1.2 new section of confidence interval for proportion of binary data |
| 1-7- | | | | |

Novartis SAP Confidential

| Date | Time point | Reason for update | Outcome for update | Section and title impacted (Current) |
|--------------------|----------------------------|--|-----------------------|---|
| | | | | Section 6 add reference related to calculation methods for exposure adjusted incidence rate and the 95% CI |
| | | | | Add reference related to calculation methods for confidence interval for proportion of binary data |
| 1- Jun- 2023 | Prior to the primary | In general the SAP was amended to | SAP Amendment 3 | Section 1 update the version of reference document |
| | analysis | align with LOU064A2301 and LOU064A2302 studies | | Section 1.1 add the statement of the data to be evaluated in interim analysis |
| | | Add lab parameters with CTCAE | | Section 2.1.1.4 update the assessment window of weight in Table 2-6 |
| | | grades | | |

Section 2.2 add definition of Screened Set as Analysis sets

Section 2.3.2 add categorical variables

Section 2.5.2 add new analysis for infections and infestations (SOC)

Section 2.6.2 delete the statement of analysis after the missing data imputation

| Novartis | Confidential | Page 6 of 54 |
|----------|--------------|------------------------|
| SAP | | Study No. CLOU064A1301 |
| | | |

| Date | Time point | Reason for update | Outcome for update | Section and title impacted (Current) |

| HSS | Hives Severity Score |
| HSS7 | Weekly Hives Severity Score |
| hrs | Hours |

| Novartis |
|----------|
| SAP |

| ICF | Informed Consent Form |
|--------|--|
| ICH | International Council for Harmonization of Technical Requirements for Pharmaceuticals for Human Use |
| lg | Immunoglobulin |
| INR | International Normalized Ratio |
| ISS | Itch Severity Score |
| ISS7 | Weekly Itch Severity Score |
| IU | International Unit |
| kg | Kilogram(s) |
| LLN | Lower Limit of Normal-range |
| LLOQ | Lower Limit of Quantification |
| MAP | Master Analysis Plan |
| MAR | Missing At Random |
| MedDRA | Medical dictionary for regulatory activities |
| m | Meter(s) |
| mg | Milligram(s) |
| mL | Milliliter(s) |
| PD | Protocol Deviation |
| | |
| | |
| | |
| | |
| | |
| PRO | Patient Reported Outcomes |
| PT | Preferred Term |
| QTcF | QT interval corrected by Fridericia's formula |
| RDO | Retrieved Drop Out |
| SAE | Serious Adverse Event |
| SAF | Safety Set |
| SAP | Statistical Analysis Plan |
| SAS | Statistical Analysis System |
| SD | Standard Deviation |
| SD | Study Discontinuation |
| SMQ | Standardized MedDRA Query |
| SOC | System Organ Class |
| TBL | Total Bilirubin |
| TFLs | Tables, Figures, Listings Shells document |
| UAS | Urticaria Activity Score |
| UAS7 | Weekly Urticaria Activity Score |
| | |
| ULN | Upper Limit of Normal-range |

| Novartis | Confidential | Page 11 of 54 |
|----------|--------------|------------------------|
| SAP | | Study No. CLOU064A1301 |

| ULOQ | Upper Limit of Quantification |
|------|-------------------------------|
| UPDD | Urticaria Patient Daily Diary |
| | |
| | |

1 Introduction

Data will be analyzed by Novartis according to the data analysis Section 12 of the CLOU064A1301 study protocol which will be made available in Appendix 16.1.1 of the Clinical Study Report (CSR). Important information is given in the following sections and details are provided, as applicable, in Appendix 16.1.9 of the CSR.

This document covers statistical and analytical plans for an interim analysis at Week 24 if conducted, and the final analysis of CLOU064A1301 study with reference to:

- the study protocol Version 01
- the case report forms (CRFs) Version 6.0
- the LOU064A master analysis plan (MAP) Version 2.0

A separate SAP for the program Data Monitoring Committee (DMC) will be prepared.

1.1 Study design

Study CLOU064A1301 is a single country, multicenter, open-label, single arm Phase 3 study investigating the safety, tolerability and efficacy of remibrutinib (25 mg b.i.d.) in Japanese adult participants with Chronic Spontaneous Urticaria (CSU) inadequately controlled by second-generation H1-antihistamines.

The study consists of three periods, the total study duration is up to 60 weeks (Figure 1-1):

- Screening period: up to 4 weeks
- **Open-label treatment period**: 52 weeks of open-label treatment with remibrutinib (25 mg b.i.d.)
- Follow-up period: 4 weeks of treatment-free follow-up (only for participants who do not enroll into the extension study)

Approximately 70 adult participants will be enrolled in the treatment period.

An interim analysis may be conducted when all participants have completed their Week 24 visit or discontinued early. The interim analysis at the time of this Week 24 database lock would be utilized for the purpose of submission to Health Authorities for marketing authorization approval. When the interim analysis is conducted, all data available at the cut-off data (beyond Week 24) will be evaluated in both efficacy and safety analysis.

Additional optional interim analyses may be conducted at the discretion of the Sponsor to support decision making concerning the current clinical study, the Sponsor's clinical development projects in general, or in case of any safety concerns. The decision to conduct the

| Novartis | Confidential | Page 13 of 54 |
|----------|--------------|------------------------|
| SAP | | Study No. CLOU064A1301 |

additional optional interim analyses and the timing/data to be reviewed will be documented in the SAP prior to the conduct of any additional optional interim analysis.

The final analysis will be conducted on all participants' data at the time the trial ends regardless of the interim analysis.

All participants will be on a stable, local label approved dose of a second-generation H1antihistamine ("background therapy") throughout the entire study (starting a minimum of 7 days prior to baseline until the end of the study). To treat unbearable symptoms of CSU, participants will be allowed to use another second-generation H1-antihistamine on an as-needed basis ("rescue therapy").

D-1: Day 1, b.i.d.: bis in die/twice a day, IA: interim analysis, mg: milligram(s), Scr: Screening, W: Week

